8.2 Expected duration of participation in the trial – Time Frame

CIS patients will be invited to join the trial for 12 months. After agreeing to join the trial, participants will be randomized into two groups. Participants in one group will receive narrow band UVB phototherapy which will be administered 3 times per week for 8 weeks. They will also wear a UVB dosimeter. Participants in the other group will not receive phototherapy but will wear a UVB dosimeter for 8 weeks. Blood will be taken from all participants for biomarker analysis at baseline (before phototherapy commences), and 1 week, and 1, 2 (ie when phototherapy ceases), 3, 6 and 12 months after initiation of phototherapy (see Appendix 1).

One group of the healthy controls will also join the trial for 12 months (those donating blood monthly). In the other group donating blood once for blood cell characterization, they will be

invited for a single blood donation.

8.3 Accountability Procedures for UVB phototherapy

Prior to commencing narrow band UVB phototherapy, a risk factor profile including previous phototherapy or PUVA treatment, sun exposure history, occupation, personal and family history of skin cancer, and medication will be ascertained. Upon examination, sun damage and presence of skin disease including skin cancers will be documented. Phototherapy will be given three times/week for eight weeks (24 exposures in total). Phototherapy will be delivered according to the Dundee protocol which is based on the patient's skin type. The starting dose of 20 mJ/cm² is chosen based on knowledge of the skin type and will be well below the likely erythema threshold. All patients will start with 40% increments on their initial dose, which will be reduced to 20% increments after 6 exposures. At each visit the dose given and any adverse effects will be recorded.

If a participant develops a confirmed second demyelinating event (confirmed relapse), the participant should be managed by Professors [name] and [name], or other neurologists associated with the study. Subjects will be withdrawn from UVB phototherapy if they experience a significant or serious adverse event, which, in the opinion of [name] or Professors [name] or [name] or other neurologists associated with the study, is related to UVB phototherapy.

The schedule is to give narrow band UVB phototherapy 3 times a week for 8 weeks Participants will be asked to exit the trial if there is more than one week between phototherapy sessions and they cannot complete 24 phototherapy sessions within 12 weeks. We will ask participants to return to the clinic for an early withdrawal/Exit visit.

8.4 Randomisation

Selection of active treatment versus control subjects will be randomised 1:1 by an independent investigator at the patient Baseline visit, with matching on demographic variables (age and sex) to optimize balance between groups. It will be obvious to the patients into which group they have been randomised.

8.5 Trial design description

Participants will be randomised to treatment, or not, with narrow band UVB phototherapy. Narrow band UVB phototherapy will be given at St John of God Medical Centre, Subiaco, Perth.

8.6 Endpoints of the study

Primary Endpoints:

- Phototherapy-associated changes in transcriptome profiling in whole blood
- Phototherapy-associated changes in the phenotype of cells in freshly isolated peripheral blood
- Phototherapy-associated changes in T regulatory cells in the peripheral blood as measured by Foxp3 expression and Foxp3 demethylation analysis
- Phototherapy-associated changes to immunological function of cells in the peripheral blood
- Development of a new demyelinating event defined as either
- A confirmed clinical relapse or
- A new cerebral T2 lesion and/or newly Gadolinium-enhancing cerebral lesion at either the 6 month or 12 month MRI scan compared to the study baseline scan.

Secondary Endpoints:

- Baseline to 12 month EDSS change
- Baseline to 12 month change in SF36 Quality of life score
- Baseline to 12 month change in Fatigue score
- Baseline to 12 month cerebral MRI grey matter volume change
- Baseline to 12 month cerebral MRI white matter volume change
- Safety: Adverse Events (including SAE) reported for UVB phototherapy

8.7 Statistical justification of participant numbers

Our power calculations assumed recruitment of 30 subjects to receive UVB phototherapy and 30 patients to not receive phototherapy (but allow study of seasonal effects). If new MRI lesions are expected in 90% of CIS patients over 1.5-2 years (CHAMPS, ETOMS, BENEFIT, PRECISE studies), then a treatment effect (ie reduction of 10%) should be discernible with a sample size of 30 patients. Power calculations for analysis of a biomarker (transcriptome) change based on standard deviation and means for each gene in winter indicated that between 11 and 27 patients need to be compared for a P<0.05.

8.8 Measures taken to minimise/avoid bias

Participants will be randomised at the screening visit by an independent investigator. It is not possible to blind the treatment group/non-treatment group, but investigators will be blind to the treatment status of participants in clinical and laboratory assessments.

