9.2 Participant insurance

If a participant becomes ill or is injured, they must immediately advise a member of the study team of their condition. In the first instance their study doctor will evaluate their condition and then discuss treatment with both the participant and their regular treating doctor. As this trial is not sponsored by a Company, any questions about compensation to the participants must initially be directed to the Co-ordinating Principal Investigator. It is the recommendation of the independent ethics committee responsible for the review of this trial that the participants seek independent legal advice. The University of Western Australia has provided indemnity cover for participants in this trial.

10. Study Assessments and Procedures

For the Schedule of Events, please refer to Appendix 1.

Professors [name] and [name], or other neurologists involved in the study, will be responsible for screening potential participants, gathering participant information, obtaining informed consent (or confirming it has been obtained by a member of the study team), determining eligibility for randomisation, clinical evaluation, clinical management of the participants during the course of the study, and review of all diagnostic blood tests and MRI results.

For those randomised to receive narrow band UVB phototherapy (and prior to phototherapy), [name] will obtain the patient's sun exposure history, occupation, personal and family history of skin cancer, and medications used. Upon examination, sun damage and presence of skin disease including skin cancers will be documented.

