10.5 Safety Assessments

Professors [name] and [name], together with [name] and designated study personnel will monitor each participant for adverse events during the study. All adverse events reported between consent and final follow-up will be recorded in the Case Report Form (CRF). Members of the project team will ask the participant non-leading questions in an effort to detect adverse events. Examples of this are:

"How are you feeling?"

Or

"Since you were last asked, have you felt unwell or different from usual?"

In addition, participants should be encouraged to spontaneously report any medical illness, or new symptoms.

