- Known co-morbid illnesses that might be exacerbated by phototherapy, including lupus erythematosus and xeroderma pigmentosum
- A history of melanoma, multiple non melanoma skin cancers
- Previous prolonged courses of UVB or photochemotherapy (PUVA), or use of sunbeds
- Cardiovascular or respiratory disease that would prevent standing in the treatment cubicle
- Bullous disease
- Use of photosensitizing medications
- Very fair skin that burns with very minimal sun exposure (as judged by the dermatologist involved)
- Current immunosuppressive drug therapy (beta-interferon, glatiramer acetate, natalizumab, mitoxantrone, or other chemotherapy agent specifically for demyelinating disease) prior to CIS diagnosis. (*Note that requirement for immunomodulatory therapy in the course of MS disease management will not exclude patients during follow-up; treatment variables will be collected and analysed in both the intervention and control arms in the planned analysis).
- Current pregnancy, breastfeeding or planning to become pregnant in the next 12 months.
- A second clinical demyelinating event prior to randomisation
- Concurrent diagnosis of other neurological, psychiatric or other disease, which, in the opinion of the investigator, could impair capacity to provide informed consent or interfere with study compliance.
- Current enrolment in another interventional trial

- Any contraindication to MRI scanning or intravenous Gadolinium including:
 - o Cardiac Pacemaker
 - Cardiac Defibrillator
 - o Metal fragments in the eye
 - o Any other non-MRI compatible medical device/implant or medical condition
 - o Previous allergic reaction to Gadolinium
 - o Severe claustrophobia

15. Withdrawal Criteria

Participants will be screened for adverse events during phototherapy, and will cease therapy if they experience a significant or serious adverse event, which, in the opinion of the treating neurologists (Professors [name] and [name]) or the dermatologist ([name]), is related to the treatment.

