18.8.2 Assessment of Causality

The Co-ordinating Principal Investigator is obligated to assess the relationship between the intervention and the occurrence of each AE/SAE, in consultation with Professors [name] and [name], and [name]. Alternative causes, such as natural history of the underlying diseases,

concomitant therapy, other risk factors, and the temporal relationship of the event to the administration of narrow band UVB phototherapy will be considered and investigated.

The causal relationship to UVB phototherapy should be assessed using the following classifications:

Not Related In the Investigator's opinion, there is not a causal relationship between UVB

phototherapy and the adverse event.

Unlikely The temporal association between the adverse event and UVB phototherapy is

such that UVB phototherapy is not likely to have any reasonable association with

the adverse event.

Possible The adverse event could have been caused by the study participants's clinical

state or UVB phototherapy.

Probable The adverse event follows a reasonable temporal sequence from the time of

UVB phototherapy, abates upon discontinuation of UVB phototherapy and cannot be reasonably explained by the known characteristics of the study

participants's clinical state.

Definitely The adverse event follows a reasonable temporal sequence from the time of

UVB phototherapy or reappears when UVB phototherapy is reintroduced.

There may be situations when an SAE has occurred and a member of the study team has minimal information to include in the initial report to the Co-ordinating Principal Investigator, and the Data Safety Monitoring Board. However, it is very important that the member of the study team always makes an assessment of causality for every event prior to transmission of the SAE form to the Co-ordinating Principal Investigator. Investigators may change their opinion of causality in light of follow-up information, amending the SAE form accordingly. The causality assessment is one of the criteria used when determining regulatory reporting requirements.

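### Section 8.8 says clinical assessments are blind, but the protocol's own role assignments contradict this for relapse and EDSS and leave it unsecured for MRI

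*Protocol*

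**What the plan says.** Section 8.8 states that the treatment groups cannot be blinded, but that "investigators will be blind to the treatment status of participants in clinical and laboratory assessments". Section 8.4 says of participants: "It will be obvious to the patients into which group they have been randomised".

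The opening of Section 10 makes the lead neurologists, or other neurologists in the study, responsible for "clinical evaluation, clinical management of the participants during the course of the study, and review of all diagnostic blood tests and MRI results". Section 8.3 provides: "Subjects will be withdrawn from UVB phototherapy if they experience a significant or serious adverse event", where the dermatologist or the neurologists consider the event related to phototherapy. Section 15 repeats this, with relatedness judged "in the opinion of the treating neurologists" or of the dermatologist, and Section 15.1 does the same. Under Section 18.8.2 the Co-ordinating Principal Investigator "is obligated to assess the relationship between the intervention and the occurrence of each AE/SAE", consulting the lead neurologists and the dermatologist. Section 10.5 says the lead neurologists, the dermatologist and designated personnel "will monitor each participant for adverse events during the study".

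Appendix 1 assigns the neurological review including EDSS to the investigator neurologist, and KFS and MSFC to the study team. Appendix 2 defines relapse by an EDSS and/or KFS rise and leaves the pseudo-relapse description to the treating physician. Section 8.6 lists confirmed relapse or a new MRI lesion among the primary endpoints, and EDSS change among the secondary ones.

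**The concern.** In an open trial with an untreated control arm, masked outcome assessment is the main protection for endpoints that rest on judgement. Here those are relapse confirmation, EDSS change and the reading of scans for new lesions. If the assessor knows the arm, expectation can move borderline calls in one arm more than in the other, and no later analysis can remove that.

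The protocol claims this protection but gives the scoring to people whose other duties reveal the arm. A reader who relies on Section 8.8 would treat the relapse and EDSS results as masked when the protocol provides no means of masking them.

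**Working it through.** The main check compares the blinding statement with the roles. It needs no arithmetic, and the protocol gives no figure on this point to reproduce.

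1. **EDSS.** Appendix 1 marks EDSS for the investigator neurologist at screening, 3, 6 and 12 months, exit and unscheduled visits. At every one of these after screening, the same code marks adverse-event reporting. Section 10.4.2 describes the 3- and 6-month appointments as being with the participant's own neurologist.
2. **Relatedness to UVB.** Sections 8.3, 15 and 15.1 let the neurologists' opinion on relatedness decide withdrawal from phototherapy, and Section 18.8.2 has the lead neurologists consulted on causality. Nobody can judge whether an event is due to phototherapy without knowing who receives it.
3. **Relapse.** Appendix 2 lets a KFS rise alone satisfy the scoring part of the definition. KFS is scored by the study team, and under Section 10.4.1 that team checks at 1 week for events caused by UVB. The treating physician's pseudo-relapse call can remove an event from the endpoint.
4. **Participants.** They know their arm (Section 8.4). Nothing tells them to keep it from the assessor.
5. **MRI.** Section 10 has the neurologists review MRI results. No section says who makes the new-lesion reading for the endpoint. Retention of digital films is stated only for the screening scan (Section 10.1).
6. **Laboratory.** Section 19.4.2 has all preparations other than fresh-blood immunophenotyping frozen and analysed at the end of the study. Masking there is feasible and nothing contradicts it.
7. **A separate rater.** Section 21.2 requires examining physicians to hold EDSS certification. It does not require them to be independent of treatment.

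**Illustration of size.** The inputs are 30 per arm (Section 8.7), equal true event rates, an assumed mean recorded rate m, and an assumed differential d in endpoint calls. Recorded events are binomial with n = 30 and rates m − d/2 and m + d/2. The rejection probability is the sum, over all pairs of counts (a, b), of P(a) × P(b) wherever the two-sided test has p ≤ 0.05. Section 19.4.2 names Fisher's exact and chi-squared tests; the pooled z-test used here is the chi-squared test without continuity correction.

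At d = 10 points the differential is 0.10 × 30 = 3 patients. With m = 75% the recorded rates are 70% and 80%.

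| Differential | Fisher | z-test |
|---|---|---|
| 0 points | 2.5% | 4.9% |
| 5 points | 4.0% | 7.2% |
| 10 points | 8.9% | 14.2% |
| 15 points | 18.4% | 26.6% |

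With m varied from 50% to 90%, the 10-point value is about 8% to 10% (Fisher) or 12% to 26% (z-test).

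Section 8.7 plans on a reduction of 10%. Read as 10 points, that is also 3 of 30 patients, so three calls moved in one arm would equal the planned effect.

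**The case against.** The strongest reply is that Section 10 gives duties to a group, not to one person per participant. Other neurologists are available, so treating and examining roles could be split in practice. The opinions that trigger withdrawal are alternatives, and the dermatologist's could suffice. Recording adverse events does not by itself reveal the arm, since Section 10.5 prescribes non-leading questions. All of this is fair. It shows that masking is possible with existing staff. It does not show that the protocol provides it, because nothing requires the split and several sections point the other way.

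A reader might infer that the claimed blinding does not exist at all. The documents do not support that. The laboratory half stands, and it bears on the four biomarker primary endpoints. A reader might also infer that the MRI endpoint is read unmasked. The protocol does not say so; it names no reader.

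The illustration has limits. Neither the 75% rate nor any size of rating bias comes from the protocol, whose only stated rate is 90% with new MRI lesions over 1.5 to 2 years. The endpoint is composite, and a new lesion alone is enough. If 90% applied, only about 0.10 × 30 = 3 patients per arm would remain for whom a relapse call alone decides the outcome, so large swings in the composite would need biased scan reading. That objection stands for the composite. It does not protect EDSS change or the separate clinical-relapse analysis listed in Section 19.4.1.

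**Conclusion.** The concern holds for clinical relapse and EDSS: the protocol states that these assessments are blind and then assigns them in ways that defeat the statement. For MRI the masking is unsecured, not disproved. For laboratory assessments there is no contradiction. This is not detail that can be left to a statistical analysis plan, because the protocol itself makes the claim and sets the roles.

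The conclusion rests on the text alone. The error rates show only what is at stake if a differential of a given size arose. They depend on the assumed event rate, the assumed bias and the test chosen, and they are not an estimate of bias in this trial. The point should be corrected before the relapse and EDSS results are presented as blind-assessed.

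**What to change.** Reconcile Sections 8.3, 8.8, 10, 10.4.1, 15, 15.1 and 18.8.2 and Appendices 1 and 2.

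1. Have EDSS, KFS and relapse or pseudo-relapse confirmation scored by an existing study neurologist or study-team member who does not manage that participant, does not collect UVB adverse-event information and does not see the UVB record. EDSS raters still need the Section 21.2 certification. Instruct participants not to disclose their arm to this assessor.
2. Extend the digital retention stated for the screening scan to the 6- and 12-month scans. Have the new-lesion endpoint read from copies with identity and arm removed, by an existing neurologist who is not treating that participant.
3. Where a role cannot be separated, withdraw the blinding claim for that assessment and report the endpoint as assessed unblinded.

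Who decides on stopping phototherapy is not at issue and should not be changed on this account. Those sections need only be made consistent with the blinding statement.

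The cost is protocol wording, some rota planning among existing staff, and the work of retaining, de-identifying and reading the follow-up scans. The third option costs only wording.

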8.9 Pilot study

There has been no pilot study.

8.10 Concepts and terminology

These have been clearly defined at the beginning of this protocol, page 6.

8.11 Principles of informed consent

All potential participants in this study must provide informed consent before any study related procedures are undertaken (including screening procedures to determine eligibility). The Patient Information Sheet will describe the purpose of the study, the procedures to be followed, and the risks and benefits of participation. It will also include the contact details of the study team that can be contacted should the participant have any questions. The recruiting neurologists will conduct the informed consent discussion and will check that the participant comprehends the information provided and answer any questions about the study at this time also. If in agreement to proceed with the study, participants will sign the Participant Informed Consent Form. Participants will be provided with a copy of the Participant Informed Consent Form and the fact that the subject has been consented to the study will be documented in the subject's record.

If potential participants wish to discuss their joining the study with their family or friends, they may request that one of the project co-ordinators contact them within a week to further discuss their participation. If they give verbal consent, a 'Baseline' visit with a member of the study team will be arranged and written consent obtained. At this visit, it will be confirmed that they are eligible to participate in the study and any questions that they have would be answered.

9. Selection of participants

All patients presenting with CIS during 2014, 2015 and 2016 will be invited to join this trial.

The healthy individuals in Perth recruited to donate blood monthly for biomarker analysis will be of similar age and sex to the CIS patients participating in the trial. At the time of their recruitment by advertisement at the Telethon Kids Institute, these individuals will have no known autoimmune disease and have not had a cold, flu or other illness in the last 7 days. They will not be taking strong immunomodulatory drugs (the taking of agents such as vitamin D, NSAIDs or aspirin will be permitted). Measurement of selected biomarkers of these healthy controls from the same city as the CIS patients will allow precise comparison of the relative extent of change in biomarker expression by UVB phototherapy, and during the different seasons of the year.

For the additional group of up to 40 age and sex matched healthy individuals in Perth donating a single blood sample for cell isolation and characterisation, up to 45 ml blood will be taken. At the time of their recruitment by advertisement at the Telethon Kids Institute, these individuals will have no known autoimmune disease and have not had a cold, flu or other illness in the last 7 days. They will not be taking strong immunomodulatory drugs (the taking of agents such as vitamin D, NSAIDs or paracetamol will be permitted). The profile of the cells in the blood of the healthy individuals will be compared with that of the CIS participants at baseline.

9.1 Participant reimbursement

Participants (including healthy individuals) will not be reimbursed for their involvement in the trial. It is anticipated to reimburse reasonable travel costs and/or provide parking vouchers.

9.2 Participant insurance

If a participant becomes ill or is injured, they must immediately advise a member of the study team of their condition. In the first instance their study doctor will evaluate their condition and then discuss treatment with both the participant and their regular treating doctor. As this trial is not sponsored by a Company, any questions about compensation to the participants must initially be directed to the Co-ordinating Principal Investigator. It is the recommendation of the independent ethics committee responsible for the review of this trial that the participants seek independent legal advice. The University of Western Australia has provided indemnity cover for participants in this trial.

10. Study Assessments and Procedures

For the Schedule of Events, please refer to Appendix 1.

Professors [name] and [name], or other neurologists involved in the study, will be responsible for screening potential participants, gathering participant information, obtaining informed consent (or confirming it has been obtained by a member of the study team), determining eligibility for randomisation, clinical evaluation, clinical management of the participants during the course of the study, and review of all diagnostic blood tests and MRI results.

For those randomised to receive narrow band UVB phototherapy (and prior to phototherapy), [name] will obtain the patient's sun exposure history, occupation, personal and family history of skin cancer, and medications used. Upon examination, sun damage and presence of skin disease including skin cancers will be documented.

